9.2.2. Sample Size Sensitivity

In order to characterize and understand the performance of the design, the study was simulated under several different scenarios.

The powers for different scenario range from 45-90% and detail result are shown in [Appendix 9](#).

Scenarios considered for the true hazard ratios for low dose and high dose DNX are shown in [Table 10](#).

Table 10 Dose-Response profile for Hazard Ratio

	DNX FBE 15 mg + OSV	DNX FBE 50mg + OSV
1. No effect	1	1
2. Small effect	1.2	1.2
3. Large effect	1.5	1.5
4. Mixed effect	1.2	1.5
5. High dose large effect	1	1.5

9.2.3. Sample Size Re-estimation or Adjustment

No sample size re-estimation is planned.

An adaptive design is employed that allows for dropping a dose at interim analyses. These interim analyses also allow for early stopping for futility or efficacy. The target

sample size is 300 subjects; if early futility or efficacy criteria are met, as few as 75-100 subjects may be enrolled. The first interim analyses will occur after the first flu season if there are more than 75 subjects enrolled. Additional interim analyses may be performed after approximately 50-66% of subjects have been enrolled.

Assuming an effective drug (HR = 1.2 and 1.5 for low and high dose respectively), there is 26% probability, the sample size is 100 subjects at the end of the study, and 67% probability the sample is less than 220. Assuming an ineffective drug (HR =1 for both doses), there is 47% probability, the sample size is 100 subjects at the end of the study, and 86% probability the sample is less than 220. Average sample size for each Dose-response profile is provided in [Appendix 9](#).

9.3. Data Analysis Considerations

9.3.1. Analysis Populations

The Intent to Treat Exposed Population (ITT-E) will consist of all randomized subjects who receive at least one dose of investigational product. Subjects will be assessed according to their randomized treatment, regardless of the treatment they receive. The ITT-E population will be used for summaries of study population and disposition.

The Influenza positive population (IPP) will consist of all subjects in the ITT-E population with influenza infection (positive influenza PCR or culture at any timepoint) confirmed by central lab testing. Unless stated otherwise, the IPP will be used as the primary population for the primary efficacy analysis and all other efficacy analyses.

The safety population will consist of all randomized subjects who receive at least one dose of investigational product. Subjects will be assessed according to their actual treatment received, regardless of the randomization assigned. This will be the primary population for safety analysis.

The Pharmacokinetic population: This population includes all subjects who underwent blood PK sampling during the study and from whom one or more blood concentration is determined. This population will be used for listing of plasma concentration-time data, non-compartmental PK and population PK analysis, as data permit.

Per Protocol Population (PP): The PP population will exclude subjects from the IPP who have no post-baseline data or who have protocol deviations that lead to exclusion from PP population. To decide which subjects should be removed from PP population, the study team will review protocol deviation prior to unblinding of the data. If warranted, the Per Protocol population will be used for sensitivity analysis in the primary efficacy comparisons

9.3.2. Interim Analysis

An Independent Data Monitoring Committee (IDMC) will review key safety data from the sentinel cohorts. Enrollment in the study will continue during IDMC review. In the first influenza season, the IDMC will continue to review unblinded safety data, after

every approximately 10-20 subjects have completed treatment in the study. Frequency of IDMC reviews in subsequent seasons will be determined based on safety results of the interim analysis.

Pharmacokinetic analysis will be done in batches during the study with special emphasis to process and analyze after each sentinel group has completed treatment, to provide an early confirmation of exposure to DNX. Similarly, to obtain early evidence of target engagement, nasal wash and/or endotracheal samples may be evaluated in batches during the study to determine neutrophil patterns following treatment with DNX.

Interim analyses of efficacy and safety data will be conducted to confirm dose regimens for subjects in the remainder of the influenza seasons. The first interim analyses will occur after the first flu season if there are more than 75 subjects enrolled. Additional interim analyses may be performed after approximately 50-66% of subjects have been enrolled.

Detail of data to be reviewed and decision criteria will be included in the IDMC charter.

9.4. Key Elements of Analysis Plan

9.4.1. Efficacy

9.4.1.1. Primary Analysis

Probability of success, denoted Prob(Success), will be calculated. Success is defined as a statistically significant treatment effect (p-value<0.025 for hazard ratio of TTCR >1) in a future two-arm comparative superiority study with 300 subjects per arm, given observed data.

Let T_0 be the time to clinical response for the control arm with exponential distribution

$$T_0 \sim \text{Exp}(\lambda)$$

Where λ is the hazard rate constant of subjects in the control arm, the parameter is modeled as:

$$\lambda \sim \text{Gamma}\left(n, \frac{n}{\mu}\right)$$

Where n is prior weight parameter and μ is prior mean parameter, we set n=4 and $\mu=0.83$ based on the hazard rate observed in study NAI114373.

Let T_d be the time to clinical response for the dose level d :

$$T_d \sim \text{Exp}(h_d)$$

where $h_d = \lambda e^{\theta_d}$, and θ_d is log-hazard ratio and modeled with independent dose-dose response model.

Kaplan-Meier estimates for the median of TTCR for each treatment group and the median difference and 95% confidence interval (CI) between DNX arms and OSV will be provided.

9.4.1.2. Secondary Analyses

Median, median difference and 95% for the median differences between DNX arms and OSV for Time to respiratory response and each component of TTCR will be provided.

Proportion of subjects with clinical response, improved respiratory status and resolution of each component of TTCR over time will be summarized.

Proportion of subjects with improvement in Ordinal scale of clinical efficacy over time will be provided.

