4.4. Design Justification

This will be the first study conducted with DNX in the hospitalized influenza population. As such the study design includes stepwise enrolment of sentinel cohorts with more stringent eligibility criteria as well as enhanced safety monitoring to assess the safety and tolerability of DNX. Following acceptable outcomes from IDMC reviews, additional subjects will be enrolled in the study.

The IV formulation of the HBr salt of DNX has been developed as treatment in this study, because parenteral administration would be a preferred mode of delivery in this hospitalized population.

All treatment groups in this study will receive open-label OSV, one of the recommended antiviral treatments for this population hospitalized for influenza [CDC, 2011; WHO, 2010]. One treatment group will receive matching IV DNX placebo as a double-blind control, while receiving open label OSV.

The primary composite endpoint of Time to Clinical Resolution (TTCR) was considered following guidelines developed by the Food and Drug Administration (FDA) for treatment of seriously ill hospitalized patients with influenza. While efficacy endpoints have not been definitively validated for all types of influenza trials, TTCR incorporates FDA guidance for inclusion of clinical signs and symptoms [FDA Guidance for Industry, 2011].

A key efficacy endpoint for this study is Time to Respiratory Resolution (TTRR) and is being evaluated as a secondary endpoint. Because DNX's mechanism of action is expected to be predominantly localized to the lung, TTRR will be analyzed to assess if it is a more relevant physiological measure. In this first study with DNX (co-administered with OSV) in hospitalized influenza, safety assessments are also a key secondary endpoint.

In alignment with the mechanism of action of DNX as an anti-inflammatory agent, which impacts the host response and not as a direct-acting antiviral, virologic endpoints are

being evaluated as exploratory endpoints. Additional exploratory endpoints include biomarkers (important in influenza infection and to demonstrate target effect) and health outcomes.

[figure not shown]

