9.2. Sample Size Considerations

9.2.1. Sample Size Assumptions

The TTCR endpoint was used in GSK Study NAI14373 (IV zanamivir), conducted in a similar population of hospitalized influenza subjects. The TTCR endpoint from NAI14373 was calculated as defined in the protocol. Median TTCR from Kaplan-Meier estimates in the oseltamivir treatment group from the confirmed influenza population are summarized (Table 8), and applied to the less severe subjects and for critically ill subjects at baseline separately. Hazard ratio estimates from the proportional hazard model of IV zanamivir vs oseltamivir range from 1.6 – 1.7 in the Mechanical ventilation at baseline sub-group in study NAI14373. Hazard ratio and clinical improvement in days over oseltamivir are provided in the table for reference.

Table 8 Hazard Ratio and Clinical Improvement over oseltamivir

Population	Median Recovery time (days)	Hazard Ratio	Clinical effect Improvement in Days
Less severe sub-population	5.8	1.2	1
		1.5	2
Critically ill sub-population	20.1	1.2	3.4
		1.5	6.7

TTCR is assumed to follow exponential distribution with constant hazard rate λ . To incorporate prior information on the oseltamivir arm, a weak informative prior of Gamma (4, 4/0.83) distribution with mean parameter of 0.83 and weight parameter of 4, will be used for λ in the oseltamivir arm. The mean and median hazard rates for the Gamma distribution are 0.83 and 0.76, respectively, with 2.5th percentile of 0.226 and 97.5th percentile of 1.819. A constant hazard rate of 0.83 for exponential distribution centers the recovery time at 5.8 days. A weight parameter of 4 provides relative small weight on the prior and will allow data to dominate the posterior, the 95% recovery time could range from 2.6 to 21.4 days to allow wide range possible outcomes. A non-informative prior will be used for DNX arms.

The sample size of 300 was selected based on simulations to achieve at least 80% overall power under assumption of HR =1.5 for 50 mg of DNX FBE and HR =1.2 for 15 mg of DNX FBE and keep type I error less than 10% under no-effect assumption.

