The study will enrol approximately 300 subjects with ratio 2:2:1 to 15mg IV DNX FBE+ OSV, 50mg IV DNX FBE + OSV and IV DNX placebo +OSV arms. An informative prior on the oseltamivir arm for the Bayesian analysis provides additional data from prior study for the control arms, combining prior data and data from this study allows us to have fewer subjects on the control arm with a 2:2:1 randomization ratio.

It is assumed that there is no difference in treatment effect between the less severe and severe population. Assuming a treatment effect of HR =1.5 for 50 mg of DNX FBE and

a clinically meaningful treatment effect of HR =1.2 for 15 mg of DNX FBE, there is an 82% chance that at least one dose will meet the success criteria described below:

At interim: Probability (success) >90%

Final: Probability (success) >50%

Assuming a HR of 1 for both doses, the overall type I error is 9%, i.e. there is a 9% chance of one or more doses being declared success incorrectly.

Table 9 Type I error by Interim and Overall

Hazard ratio	Type I error for Interim 1 n=100	Type I error for Interim 2 n=200	Overall Type I Error
Criteria	Probability (success) >90%	Probability (success) >90%	Probability (success) >50%
L: HR=1 H: HR=1	1%	0%	9%

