9.4.1.3. Subgroup Analyses

To evaluate the benefit of DNX in a sub-population, one key subgroup has been pre-specified for evaluation of efficacy.

- **Disease severity at baseline:** Patients requiring CPAP (i.e. new use for respiratory distress and not for chronic purposes such as sleep apnea), BIPAP, mechanical ventilation, those who have hemodynamic instability (with or without pressor support), or have central nervous system involvement (eg encephalopathy, encephalitis) are considered a more severe population.

Additional subgroups will be pre-specified in the reporting analysis plan.

The KM estimates for the primary analysis and key secondary analyses will be repeated by the subgroups.

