8. SECONDARY STATISTICAL ANALYSES

8.1. Efficacy Analyses

8.1.1. Overview of Planned Efficacy Analyses

The secondary efficacy analyses will be based on the IPP population, unless otherwise specified. Table 5 provides an overview of the planned efficacy analyses, with full details of data displays being presented in Appendix 13: List of Data Displays. Given the small number of subjects, only time to respiratory response will be summarized. Data relevant to other secondary endpoints will be listed including vital signs, ventilation status, hospital discharge, hospital re-admission, and ICU stay.

Table 5 Overview of Planned Secondary Efficacy Analyses

Endpoint	Stats Analysis			Analysis Summary		ummary Individua	
	Т	F	L	T	F	F	L
	Absolute						
Time to Respiratory Response (TTRR)				Y [1]			

^[1] Proportion of clinical response and Kaplan Meier estimates for the median of TTCR for each treatment group and the median difference and 95% CI between two comparisons: each DNX arm and OSV will be provided

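### The protocol compares TTRR and the TTCR components between arms only by medians; a severity-stratified hazard ratio alongside would use about twice the information under the plan's own model

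*Protocol*

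**What the plan says.** Protocol section 4.4 gives TTRR a special place: "A key efficacy endpoint for this study is Time to Respiratory Resolution (TTRR) and is being evaluated as a secondary endpoint". The reason given is that the drug is expected to act mainly in the lung, so TTRR might be the more relevant measure.

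For the comparison between arms, section 9.4.1.2 lists "Median, median difference and 95% for the median differences between DNX arms and OSV for Time to respiratory response", and the same for each TTCR component. I read the bare 95% as a 95% interval. The section adds "Proportion of subjects with clinical response, improved respiratory status and resolution of each component of TTCR over time will be summarized", which is descriptive. Section 9.4.1.3 names disease severity as the one key subgroup and says "The KM estimates for the primary analysis and key secondary analyses will be repeated by the subgroups".

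TTCR is treated differently. Section 9.4.1.1 models it as exponential with a log hazard ratio for each dose and defines success in a future study by "p-value<0.025 for hazard ratio of TTCR >1". The same section also plans Kaplan-Meier medians and a median difference with 95% interval for TTCR.

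The SAP was written after the study stopped with 10 subjects and makes every analysis descriptive. Its synopsis lists the TTRR median and 95% interval. The note to its Table 5 still says "the median difference and 95% CI between two comparisons: each DNX arm and OSV will be provided", although that note sits on the TTRR row and its wording refers to TTCR.

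**The concern.** The plan already holds a model for response times in which the treatment effect is a constant hazard ratio. Under that model the sample median uses only about half the information on the effect. Using it as the sole between-arm measure makes the interval for a key endpoint much wider than it need be.

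Severity adds to this. Protocol Table 8 puts the control median at 5.8 days in less severe subjects and 20.1 days in the critically ill, and severity is not among the minimization criteria in section 6.2. A pooled median difference takes no account of that spread. At stake is how often a real respiratory effect, overall or within a severity subgroup, would be left looking inconclusive.

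**Working it through.** **Inputs**
- Effect: hazard ratio (HR) 1.5 for 50 mg and 1.2 for 15 mg, from section 9.2.1 ("achieve at least 80% overall power under assumption of HR =1.5 for 50 mg of DNX FBE and HR =1.2 for 15 mg"). These are TTCR values, and the documents give none for TTRR, so using them for TTRR is an assumption.
- Arms: "The study will enrol approximately 300 subjects with ratio 2:2:1" gives 120, 120 and 60, so one dose v placebo is 120 v 60 if no arm is dropped and the trial does not stop early.
- Times: exponential, control median 5.8 days (section 9.2.1); follow-up to Day 45 (section 4.2).
- Criterion: a two-sided 95% interval excludes no effect. No test of TTRR is planned, so power below means only this.

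**The plan's own figures.** There is no stated power for TTRR to reproduce; the 82% in section 9.2.1 belongs to the TTCR success rule. Table 8 can be reproduced. Under exponential times the treated median is the control median divided by the HR. So 5.8 - 5.8/1.5 = 1.93 days (stated as 2), 5.8 - 5.8/1.2 = 0.97 (stated as 1), 20.1 - 20.1/1.5 = 6.7 and 20.1 - 20.1/1.2 = 3.35 (stated as 3.4).

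**Hazard ratio, HR 1.5.** The control hazard is ln 2/5.8 = 0.1195 per day. The share of controls without response at Day 45 is exp(-0.1195 x 45), about 0.5%, so there are about 180 events.
- z = ln(1.5) x sqrt(180 x 1/3 x 2/3) = 0.4055 x 6.325 = 2.564
- Power = Phi(2.564 - 1.960) = 72.7%. Simulated log-rank (3,000 trials): 71.6%.

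**Difference in sample medians, HR 1.5.** For exponential times, var(median) = 1/(n x hazard^2).
- Placebo: (5.8/ln 2)^2/60 = 1.167. Active: (3.867/ln 2)^2/120 = 0.259.
- SE = sqrt(1.426) = 1.19 days, so the 95% interval is about +/-2.3 days around a true difference of 1.93.
- z = 1.93/1.19 = 1.62; power = Phi(1.62 - 1.96), about 36.7%.
- On the log scale, efficiency against the log hazard ratio is (ln 2)^2 = 0.48. z = 2.564 x 0.693 = 1.777; power 42.8%. Simulation with a bootstrap interval: 41.2%.

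**If the median difference means a Hodges-Lehmann shift.** Its interval inverts the rank-sum test, whose efficiency here is 0.75. z = 2.564 x sqrt(0.75) = 2.221; power about 60%.

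**Severity mix (simulated, HR 1.5 within each stratum).** The documents give no share of critically ill subjects, so 30% is an assumption.

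| Measure | 30% critically ill | 10-50% critically ill |
|---|---|---|
| Median difference | about 36% | 34-39% |
| Log-rank, unstratified | about 50% | 49-57% |
| Log-rank, severity-stratified | about 67% | 67-69% |

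Pooling two exponential groups with different medians breaks proportional hazards in the pooled data, which is why stratification recovers so much.

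**Other sensitivities**
- With 171, 162 or 144 events, HR power is 70.5%, 68.2% or 63.1%.
- Scaling to the average sample size of 207 in Table 12 gives 180 x 207/300, about 124 events. HR power is then 57%; the median difference on the log scale gives Phi(1.475 - 1.960), about 31%.
- At HR 1.2 with 180 events: 21% for the HR against about 12% for the median difference.

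**The case against.** The strongest reply is that a phase 2 secondary endpoint may properly be reported in days. Medians are easy to read, need no proportional hazards, and Table 8 itself translates hazard ratios into days. Section 9.4 sets out only key elements of the analysis. That supports keeping the medians; it does not explain leaving out a measure that the plan already uses for TTCR.

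Two stronger readings are tempting, and the documents support neither.
- A reader might infer that the trial cannot compare TTRR with TTCR because they are on different scales. Section 9.4.1.1 plans a median difference with 95% interval for TTCR too, so a like-for-like comparison exists, at about half the available information.
- A reader might infer that the plan cuts a stated power from about 72% to about 40%. No test, effect size or power is stated for TTRR. The figures borrow TTCR inputs, and the median estimator is not specified.

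Other parts of the reply also stand. The 73% assumes full arms of less severe subjects. Efficacy is analysed in centrally confirmed influenza cases (section 9.3.1), so the arms may be smaller. With 30% critically ill, an unstratified hazard comparison gains only about 14 points over the median difference; the rest of the gain comes from stratifying. At HR 1.2 neither measure is informative.

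**Conclusion.** The point holds as a matter of precision in the protocol's full-enrolment plan. The only between-arm comparison specified for TTRR and the TTCR components is the median difference, and the severity subgroup gets only Kaplan-Meier estimates.

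On borrowed TTCR assumptions at HR 1.5 and 120 v 60, the chance of an interval that excludes no effect is about 37-43% for a difference in sample medians (about 60% for a Hodges-Lehmann shift), against about 73% for a hazard ratio. With an assumed 30% critically ill it is about 36%, against 50% unstratified and 67% stratified. The size therefore depends on the estimator, the case mix and the number enrolled, but the hazard ratio did better in every setting examined.

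A reader might also infer that the SAP is deficient here. It is not: with 10 subjects, no formal testing and no subgroups, no planned inference is weakened.

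**What to change.** In protocol section 9.4.1.2, add for TTRR and for each TTCR component a hazard ratio with 95% interval for each DNX arm v placebo, from a Cox model stratified by baseline severity. Keep the Kaplan-Meier medians and the median difference alongside, and name the estimator and interval method for that difference. In section 9.4.1.3, report the TTCR and TTRR hazard ratios within each severity subgroup.

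The cost is a wording change and one model per endpoint, with no new data or subjects. The downside is reliance on proportional hazards. Section 9.4.1.1 already assumes them for TTCR, and section 9.2.1 assumes the same treatment effect in both severity groups; the Kaplan-Meier display remains as a check. The 10-subject SAP report can stay as it is.

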9.4.1.3. Subgroup Analyses

To evaluate the benefit of DNX in a sub-population, one key subgroup has been pre-specified for evaluation of efficacy.

- **Disease severity at baseline:** Patients requiring CPAP (i.e. new use for respiratory distress and not for chronic purposes such as sleep apnea), BIPAP, mechanical ventilation, those who have hemodynamic instability (with or without pressor support), or have central nervous system involvement (eg encephalopathy, encephalitis) are considered a more severe population.

Additional subgroups will be pre-specified in the reporting analysis plan.

The KM estimates for the primary analysis and key secondary analyses will be repeated by the subgroups.

9.4.2. Safety Analysis

All safety analyses will be based on the Safety Population defined in Section 9.3.1.

Exposure to study medication, measured by the number of days on study drug, will be summarized by treatment arm. The proportion of subjects reporting adverse events (AEs) will be tabulated for each treatment arm. The following summaries of AEs will be provided:

Incidence and severity of All AEs;

Incidence and severity of treatment related AEs;

Incidence and severity of AEs leading to withdrawal from study;

Incidence of serious AEs (SAEs).

Laboratory data, vital signs and ECG data (absolute values and change from Baseline) will be summarized by visit and treatment group. In addition, the maximum post-baseline toxicity grade will be tabulated by treatment.

9.4.3. Virology Analyses

Change from baseline in influenza viral load by qRT-PCR and by quantitative virus culture from nasopharyngeal swabs will be summarized and plotted by treatment and visit. Summary of proportion of subjects with no detectable influenza viral RNA by qRT-PCR and by quantitative virus culture from nasopharyngeal swabs.

